### **12.4 Progression**

Progression is defined from the end of treatment to first local, regional/nodal or distant recurrence event, or death.

### **12.5 Disease Specific Mortality**

Disease specific mortality is defined from the end of treatment to death from disease. Deaths due to other causes will be regarded as competing risks.

### **12.6 Overall Survival**

Overall survival is defined from the end of treatment to death from any cause.

### **13.1 CRITERIA FOR REMOVAL FROM STUDY**

If at any time the patient develops locally progressive disease, s/he will be taken off study and referred for alternative therapy. If at any time the patient develops unacceptable toxicity, s/he will be removed from the study. If at any time the patient dies while on study, s/he will be removed from the study. If grade 3 toxicity persists, requiring a break of more than five consecutive treatments, the participant will be taken off protocol therapy. We will, however, continue to follow them for the protocol.

The primary endpoint of which the power calculation is based on number of patients needed to observe a difference in local control following surgery then chemoradiation compared to historic rates of chemoradiation alone. Patients who are taken off study due to unacceptable toxicities will not be replaced as they will be counted as failures towards the primary endpoint. Patients who are lost to follow-up do not need to be replaced as they will be counted towards failures towards the primary endpoint. The chance of patients lost to follow-up (3 months from end of chemoradiation) is extremely low as all patients in our experience will return to see us for their first post-treatment follow-up visit. If at any time the patient is found to be ineligible for the protocol as designated in the section on Criteria for Patient/Subject Eligibility (i.e. a change in diagnosis), the patient will be reviewed and determined whether to keep on study or not at the discretion of the treating physician.

A patient has the right to withdraw from the study at any time for any reason without prejudice to his/her future medical care by the physician, or at the institution. Should a patient (or a patient's legally authorized representative) decide to withdraw, all efforts will be made to complete and report the observations as thoroughly as possible. A complete final evaluation should be made at the time of the patient's withdrawal. Patients will be removed from one or more parts of the study, at the Investigator's discretion, if one or more of the following events occur:

- Significant noncompliance on the part of the patient
- Refusal of the patient to continue treatment or observations
- Decision by the Investigator that termination is in the patient's best medical interest
- Patient is lost to follow-up 6 months post registration

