### **14.0 BIOSTATISTICS**

A one-stage design will be used for this trial. Of the 25 patients to be enrolled, 15 will be SCC patients and the remaining 10 will be ACC, Esthesio, or Adenocarcinoma. Based on historical data, current standard non-surgical treatment has a 1-year local failure rate of 40% for SCC patients and 65% for ACC, Esthesio or Adenocarcinoma patients. Therefore, a mixed cohort of 15 SCC and 10 ACC/Esthesio/Adenocarcinoma patients should have 1-year local failure rate of 50% under standard non-surgical treatment. We expect to decrease such a rate to 25% using the proposed new treatment. This design depends on a one-arm, one-sided binomial test and has a decision rule as follows: If, among the total 25 patients enrolled, we have at least 17 patients who are alive, followed and local failure free (or equivalently, at most 8 patients who are dead, lost to follow up or withdrew from the study, or have local failure) one year from the end of the treatment, then we shall declare the proposed treatment strategy

worthy of further investigation. Any patient who is taken off study due to unacceptable toxicities or lost to follow up, dies or withdraws within one year from the end of treatment will be regarded as a local failure. Patients who die during treatment will also be counted as failures, though such a probability will be small. This design has a type 1 error rate of 0.05 and type 2 error rate of 0.15 for testing the hypothesis  $p \geq 50\%$  vs  $p < 25\%$ , where  $p$  represents the 1-year local failure rate.

To assess the complications of minimally invasive endoscopic skull base surgery in patients with unresectable disease, we will use Clavien-Dindo classification of surgical complications and summarize the grades (I-V) and types. This will be done after surgery but before radiation.

To assess acute and long-term toxicity of radiotherapy, we will summarize the CTCAE v4.03 scores and present descriptive statistics. This will be done weekly throughout RT, at the end of RT, and then 3 months after the end of RT for acute toxicities. Long-term toxicities will be assessed at 6, 12 and 24 months after the end of RT.

Patient reported outcomes of toxicity due to radiotherapy, EORTC (H&N43 and QLQ C30) and SBI, will be summarized and reported at the following time points: After surgery (pre RT), week 4 of RT (+/- 7 days), 1 week within end of RT, and then at 3, 6, 12 and 24 months after the end of RT.

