Specifically, the following subscales for the QLQ will be summarized at each time point.

For EORTC C30, we will look at 15 distinct groupings. These scales are: Global Health Status/QoL scale 2 items (29,30); Physical Functioning, 5 items (1-5); Role Functioning, 2 items (6,7); Emotional Functioning, 4 items (21-24); Cognitive Functioning, 2 items (20,25); Social Functioning, 2 items (26,27); Fatigue, 3 items (10,12,18); Nausea and Vomiting, 2 items (14,15); Pain, 2 items (9,19); 6-single item symptom scores (Dyspnea (8); Insomnia (11); Appetite Loss (13); Constipation (16); Diarrhea (17); and Financial Difficulties (28); all from single items).

For EORTC H&N43, we will look at 19 distinct groupings. Swallowing, 4 items (35, 36, 37, 38); Salivating, 2 items (42,43); Senses, 2 items (44,45); Speech, 5 items (47, 55, 56, 57, 58); Social eating, 4 items (51, 52, 53, 54); Pain, 4 items (31, 32, 33, 34); Anxiety, 2 items (69, 70); Body image, 3 items (48,49, 50); Teeth, 3 items (39,40, 73); Skin, 3 items (65,66, 67); Shoulder problems, 2 items (62, 63); Physical contact, 2 items (60, 61); 7-Single item symptom scores (Mouth opening (41), coughing (46), neurology (72), social contact (59), weight low (68), lymphadema (64), problems with wound healing(71)).

For SBI, we have 11 disease-specific domains/scales: Emotional, 4 items (35,36,37,38); Social, 4 items (23,28,29,32); Other Physical, 6 items (8,11,15,18,19,24); Cognitive, 4 items (12,13,21,22); Family, 3 items (31,34,40); Financial, 2 items (30,39); Spiritual, 2 items (33,41); Endocrine, 4 items (7,25,26,27); Nasal, 4 items (2,3,14,16); Neurologic, 4 items (1,9,10,20); Visual, 4 items (4,5,6,17). A composite score assuming equivalent weighting of domains in overall quality of life will also be created by averaging domain scores and summarized.

Overall survival and progression free survival will be evaluated by Kaplan-Meier method. Regional/nodal progression, distant metastasis progression and disease specific death will be evaluated by cumulative incidence function where death without event or not due to disease will be classified as a competing risk. We will also report, if feasible, all 1- and 2-year rates.

For the correlative studies, we will collect tissue samples from patients and bank them for future investigations. No statistical analyses are planned.

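### Survival follow-up after local progression is not clearly secured, and deaths before end of treatment have no place in the secondary time-to-event endpoints

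*Combined protocol and SAP*

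**What the plan says.** Section 13.1 uses two terms for removal. For local progression: "If at any time the patient develops locally progressive disease, s/he will be taken off study and referred for alternative therapy". For a grade 3 toxicity that forces a break of more than five treatments, the patient comes off protocol therapy only. The next sentence reads "We will, however, continue to follow them for the protocol". Later in 13.1, for patients who choose to withdraw, "all efforts will be made to complete and report the observations as thoroughly as possible".

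Section 14.0 has rules for the primary endpoint. "Any patient who is taken off study due to unacceptable toxicities or lost to follow up, dies or withdraws within one year" of end of treatment is a local failure, and "Patients who die during treatment will also be counted as failures, though such a probability will be small". Section 4.2 also counts a death during treatment as a failure.

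For the secondary endpoints, section 14.0 names methods only: "Overall survival and progression free survival will be evaluated by Kaplan-Meier method". For the cumulative incidences it says "disease specific death will be evaluated by cumulative incidence function where death without event or not due to disease will be classified"; these deaths are competing risks. It gives no censoring rule. "Overall survival is defined from the end of treatment to death from any cause" (12.6). Locoregional failure, distant metastasis, progression and disease-specific mortality (12.2 to 12.5) have the same origin. The secondary objectives in section 2.1 promise 1- and 2-year rates of OS, progression-free survival (PFS), disease-specific mortality, and regional and distant progression.

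**The concern.** **Follow-up after local progression.** The follow-up sentence directly follows the toxicity rule, so it may cover only those patients. If follow-up of local progressors stops when they go off study, Kaplan-Meier censors OS at local failure. These patients are likely to have a higher risk of death than the rest, so the censoring is informative and OS is overstated. Deaths from disease and regional or distant events after local failure are missed.

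**Events before the origin.** Surgery, a postoperative MRI at 3 to 5 weeks (Table 3) and about 7 weeks of radiation (9.2.6) come before end of treatment. That is at least about 10 to 12 weeks from surgery, if radiation starts straight after the MRI. A patient who dies in that window is a failure in the primary endpoint but has no defined place in OS, PFS or disease-specific mortality. Leaving such patients out makes those estimates conditional on surviving treatment.

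In both cases two analysts could follow the text and report different rates from the same trial.

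**Working it through.** **1. The plan's own design figures.** With 25 patients, success at 17 or more, and failure rates of 50% against 25%, the exact binomial type 2 error is 0.1494 (stated 0.15). The type 1 error is 0.0539, or 0.0483 with strata fixed at 15 and 10 (stated 0.05). The null mix is (15 × 0.40 + 10 × 0.65)/25 = 0.50. None of this depends on the present point.

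**2. Endpoints exposed to loss after local progression.** Local progression is already a failure in the primary endpoint and already a PFS event, so neither is affected. OS, disease-specific mortality, and regional and distant incidence are.

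**3. Size for OS.** The documents give no hazards, so these are assumptions:
- Local failure or death is 25% at 1 year. This is the section 14.0 target, which already counts deaths as failures. Withdrawals and other losses, which it also counts, are ignored here.
- Death without local failure is b = 5% a year (range 5 to 10%).
- Median survival after local failure is m = 1 year (range 0.5 to 2).
- Hazards are constant.

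Central hazards: μ = −ln(0.95) = 0.0513; λ = −ln(0.75) − μ = 0.2877 − 0.0513 = 0.2364; ν = ln 2 = 0.6931.

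True OS(t) = e^(−(λ+μ)t) + λ[e^(−νt) − e^(−(λ+μ)t)]/(λ+μ−ν):
- 1 year: 0.75 + 0.2364 × (0.50 − 0.75)/(−0.4055) = 0.896
- 2 years: 0.5625 + 0.2364 × (0.25 − 0.5625)/(−0.4055) = 0.745

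Let a fraction f of progressors be lost at local failure, P0 be the probability of being alive without local failure, and P1 of being alive after it. Kaplan-Meier then estimates survival with hazard [μP0 + ν(1−f)P1]/[P0 + (1−f)P1]. At f = 1 this is e^(−μt), that is 0.950 and 0.9025.

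| Progressors lost | Overstatement, 1 year (points) | Overstatement, 2 years (points) |
|---|---|---|
| none | 0 | 0 |
| half | 2.5 | 6.7 |
| all | 5.4 | 15.8 |

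Over the ranges of b and m, full loss gives 1.7 to 9.2 points at 1 year and 5.4 to 23.2 at 2 years.

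For scale, the approximate 95% half-width 1.96√(S(1−S)/25) is 12.0 points at 1 year and 17.1 at 2 years.

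**4. Patients affected.** Cumulative local failure is [λ/(λ+μ)](1 − 0.75^t) = 0.205 and 0.360. Times 25, that is about 5 patients by 1 year and 9 by 2 years.

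**5. Disease-specific mortality.** Deaths after local failure are total deaths minus deaths without it, the latter being [μ/(λ+μ)](1 − 0.75^t). At 1 year 0.104 − 0.045 = about 6%; at 2 years 0.255 − 0.078 = about 18%. This is the part exposed to loss.

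**6. Early deaths.** Counting one of 25 at time zero multiplies survival by 24/25, so omitting it raises OS by S/25: 0.896/25 = 3.6 points at 1 year and 0.745/25 = 3.0 at 2 years. With no early deaths the effect is 0.

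**The case against.** The strongest reply is that the protocol already intends continued follow-up. The follow-up sentence closes a paragraph that lists every removal trigger, and its plural pronoun can cover all living patients in that list. OS is death from any cause, and section 11.6 puts deaths from progression into the efficacy analyses. Stopping follow-up at local progression would defeat much of the secondary objective. This stands as evidence of intent, so a reader who infers that the protocol stops all follow-up at local progression goes too far. But none of these places says that vital status, cause of death or later events are collected from a patient who is off study and referred elsewhere.

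On early events, section 9.6 ends treatment at progression, so a progressor could be given an end-of-treatment date near that time. Table 3 schedules no tumour MRI after the postoperative one, so early progression would seldom be documented. Both remarks stand. They leave deaths before end of treatment as the main gap, and section 14.0 expects few of those.

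Three other inferences are not supported:
- Taking the 25% as local failure alone, with deaths added, gives 2.9 and 7.6 points at half loss and 6.5 and 18.6 at full loss. Section 14.0 already counts deaths within its failure rate.
- Disease-specific mortality need not fall to zero under full loss. A model that lets disease deaths occur only after local failure forces that result, but deaths from regional or distant disease without local failure remain observed.
- Sections 9.6 and 13.1 do not conflict: the first governs treatment, the second study status.

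**Conclusion.** The point holds as an unclear removal rule and a missing rule for early deaths, and it should be fixed. The text allows two readings of follow-up after local progression, and the literal off-study reading biases OS upwards and under-counts disease-specific deaths and later regional or distant events. The central overstatement of OS runs from 0 to 15.8 points at 2 years, depending on how many progressors are lost. Half loss stays within sampling error for 25 patients; full loss comes close to it at 2 years in the central case and exceeds it at the top of the range. These sizes rest on hazards and loss fractions that the documents do not give. Only the 25% anchor and the sample size are the plan's own.

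All the affected quantities are descriptive secondary estimates. The primary endpoint, sample size, error rates and decision rule do not change.

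**What to change.** 1. In section 13.1, state that removal for local progression or toxicity does not end outcome follow-up. Vital status, cause of death and regional or distant progression are collected to 24 months unless consent is withdrawn. When treatment stops is left to the investigators.
2. In section 14.0, state that OS and disease-specific mortality are not censored at local progression.
3. Keep end of treatment as the origin but include all enrolled patients. Count deaths, and any documented progression, before that date as events at time zero in the endpoints they belong to. Early deaths not due to disease enter the cumulative incidences as competing events at time zero. This is one convention among several; what matters is that one is fixed in advance.

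The cost is a few sentences, plus chart review or phone contact for about 5 patients by 1 year and 9 by 2 years in the central case. OS and disease-specific mortality may look slightly less favourable than under the reading that stops follow-up. Follow-up that was never collected may be hard to recover later, so the wording should be settled early.

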### **14.0 BIOSTATISTICS**

A one-stage design will be used for this trial. Of the 25 patients to be enrolled, 15 will be SCC patients and the remaining 10 will be ACC, Esthesio, or Adenocarcinoma. Based on historical data, current standard non-surgical treatment has a 1-year local failure rate of 40% for SCC patients and 65% for ACC, Esthesio or Adenocarcinoma patients. Therefore, a mixed cohort of 15 SCC and 10 ACC/Esthesio/Adenocarcinoma patients should have 1-year local failure rate of 50% under standard non-surgical treatment. We expect to decrease such a rate to 25% using the proposed new treatment. This design depends on a one-arm, one-sided binomial test and has a decision rule as follows: If, among the total 25 patients enrolled, we have at least 17 patients who are alive, followed and local failure free (or equivalently, at most 8 patients who are dead, lost to follow up or withdrew from the study, or have local failure) one year from the end of the treatment, then we shall declare the proposed treatment strategy

worthy of further investigation. Any patient who is taken off study due to unacceptable toxicities or lost to follow up, dies or withdraws within one year from the end of treatment will be regarded as a local failure. Patients who die during treatment will also be counted as failures, though such a probability will be small. This design has a type 1 error rate of 0.05 and type 2 error rate of 0.15 for testing the hypothesis  $p \geq 50\%$  vs  $p < 25\%$ , where  $p$  represents the 1-year local failure rate.

To assess the complications of minimally invasive endoscopic skull base surgery in patients with unresectable disease, we will use Clavien-Dindo classification of surgical complications and summarize the grades (I-V) and types. This will be done after surgery but before radiation.

To assess acute and long-term toxicity of radiotherapy, we will summarize the CTCAE v4.03 scores and present descriptive statistics. This will be done weekly throughout RT, at the end of RT, and then 3 months after the end of RT for acute toxicities. Long-term toxicities will be assessed at 6, 12 and 24 months after the end of RT.

Patient reported outcomes of toxicity due to radiotherapy, EORTC (H&N43 and QLQ C30) and SBI, will be summarized and reported at the following time points: After surgery (pre RT), week 4 of RT (+/- 7 days), 1 week within end of RT, and then at 3, 6, 12 and 24 months after the end of RT.

Specifically, the following subscales for the QLQ will be summarized at each time point.

For EORTC C30, we will look at 15 distinct groupings. These scales are: Global Health Status/QoL scale 2 items (29,30); Physical Functioning, 5 items (1-5); Role Functioning, 2 items (6,7); Emotional Functioning, 4 items (21-24); Cognitive Functioning, 2 items (20,25); Social Functioning, 2 items (26,27); Fatigue, 3 items (10,12,18); Nausea and Vomiting, 2 items (14,15); Pain, 2 items (9,19); 6-single item symptom scores (Dyspnea (8); Insomnia (11); Appetite Loss (13); Constipation (16); Diarrhea (17); and Financial Difficulties (28); all from single items).

For EORTC H&N43, we will look at 19 distinct groupings. Swallowing, 4 items (35, 36, 37, 38); Salivating, 2 items (42,43); Senses, 2 items (44,45); Speech, 5 items (47, 55, 56, 57, 58); Social eating, 4 items (51, 52, 53, 54); Pain, 4 items (31, 32, 33, 34); Anxiety, 2 items (69, 70); Body image, 3 items (48,49, 50); Teeth, 3 items (39,40, 73); Skin, 3 items (65,66, 67); Shoulder problems, 2 items (62, 63); Physical contact, 2 items (60, 61); 7-Single item symptom scores (Mouth opening (41), coughing (46), neurology (72), social contact (59), weight low (68), lymphadema (64), problems with wound healing(71)).

For SBI, we have 11 disease-specific domains/scales: Emotional, 4 items (35,36,37,38); Social, 4 items (23,28,29,32); Other Physical, 6 items (8,11,15,18,19,24); Cognitive, 4 items (12,13,21,22); Family, 3 items (31,34,40); Financial, 2 items (30,39); Spiritual, 2 items (33,41); Endocrine, 4 items (7,25,26,27); Nasal, 4 items (2,3,14,16); Neurologic, 4 items (1,9,10,20); Visual, 4 items (4,5,6,17). A composite score assuming equivalent weighting of domains in overall quality of life will also be created by averaging domain scores and summarized.

Overall survival and progression free survival will be evaluated by Kaplan-Meier method. Regional/nodal progression, distant metastasis progression and disease specific death will be evaluated by cumulative incidence function where death without event or not due to disease will be classified as a competing risk. We will also report, if feasible, all 1- and 2-year rates.

For the correlative studies, we will collect tissue samples from patients and bank them for future investigations. No statistical analyses are planned.

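### Can the one-year decision rule give two answers when a patient is removed for a reason that Section 14.0 does not list?

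*Combined protocol and SAP*

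**What the plan says.** Section 14.0 sets a one-stage, one-sided binomial test in 25 patients, 15 with squamous cell carcinoma and 10 with the other histologies. The main clause of the decision rule asks whether "among the total 25 patients enrolled, we have at least 17 patients who are alive, followed and local failure free" one year from the end of treatment. A bracket restates it: "or equivalently, at most 8 patients who are dead, lost to follow up or withdrew from the study, or have local failure". The next sentences widen the failure class to take in this group: "Any patient who is taken off study due to unacceptable toxicities or lost to follow up, dies or withdraws within one year". That year is counted once therapy has finished. Deaths during treatment are failures too. On operating characteristics: "This design has a type 1 error rate of 0.05 and type 2 error rate of 0.15", for failure rates of 50% against 25%.

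Section 13.1 lists further ways off study. "Patients will be removed from one or more parts of the study, at the Investigator's discretion", for reasons that include "Significant noncompliance on the part of the patient" and "Decision by the Investigator that termination is in the patient's best medical interest". For a patient found ineligible after entry, "the patient will be reviewed and determined whether to keep on study or not at the discretion of the treating physician". Section 13.1 states failure status without replacement only for toxicity removals and losses to follow-up.

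**The concern.** A success count and a failure count are interchangeable only if every enrolled patient falls in exactly one of them. Three of the Section 13.1 exits (ineligibility, noncompliance, investigator decision) have no stated endpoint status. A patient who leaves by one of them and is no longer followed cannot be among the 17, yet is in no failure class that Section 14.0 names.

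The word for withdrawal does not plainly cover these patients. Section 13.1 uses it for the patient's own decision and speaks of removal when the investigator acts. Section 14.0 lists toxicity removal separately from withdrawal.

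This is the trial's only formal decision, in an uncontrolled study, and the exits are discretionary. If the result sat on the boundary, the conclusion could turn on which form the analyst applied, and the lenient form would carry a size above the stated 0.05.

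**Working it through.** **Inputs (Section 14.0).** N = 25. Null failure rate: (15 × 0.40 + 10 × 0.65) / 25 = 12.5 / 25 = 0.50. Alternative: 0.25. Cut-off: at most 8 failures, that is, at least 17 successes. The number of patients removed by the three routes and not followed, u, is not in the documents; u = 1 and u = 2 are assumptions, with removal unrelated to outcome.

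**The plan's own figures.** With X the number of failures:

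- Size: P(X ≤ 8 | 25, 0.50) = 0.0539. With the two strata at 40% and 65% it is 0.0483.
- Power: P(X ≤ 8 | 25, 0.25) = 0.8506, so the type 2 error is 0.1494.

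The printed 0.05 and 0.15 hold at two decimals.

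**Counterexample.** 16 successes + 8 named failures + 1 removed for noncompliance and not followed = 25. The count of 16 misses 17; the count of 8 meets 8. Read literally, the forms conflict.

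**Operating characteristics.** Let m = 25 − u be the patients with a status. The success form needs at least 17 successes among m, so X ≤ m − 17 = 8 − u. The failure form needs X ≤ 8 among m. They disagree when 8 − u < X ≤ 8.

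| u | m | Success form: size / power | Failure form: size / power | Disagree at 50% / 25% |
|---|---|---|---|---|
| 0 | 25 | 0.0539 / 0.8506 | 0.0539 / 0.8506 | 0 / 0 |
| 1 | 24 | 0.0320 / 0.7662 | 0.0758 / 0.8787 | 0.0438 / 0.1125 |
| 2 | 23 | 0.0173 / 0.6537 | 0.1050 / 0.9037 | 0.0877 / 0.2500 |

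The last column is conditional on u such removals having occurred. If instead each patient independently had a 2% chance of one (an assumption), the forms would disagree with probability 0.022 at a 50% failure rate and 0.059 at 25%.

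**Which form governs.** Three features of Section 14.0 settle it.

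1. The denominator is all enrolled patients, so nobody drops out of it by being removed.
2. Success is defined positively and requires follow-up. A removed, unfollowed patient does not qualify, whatever the reason for removal.
3. The failure list is a bracket that the plan itself offers as the same rule in other words. An illustrative list that is two or three categories short does not displace the clause it restates.

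**Which direction the gap runs.** Without replacement, removing a patient can never add a success. Under the governing form, discretionary removal can therefore only count against the treatment, and size stays at or below 0.0539 even if removal depends on outcome. The power figures of 0.77 and 0.65 are the price of counting every unknown as a failure, and rewriting the bracket to say so would give the same figures. The only inflation, 0.076 or 0.105, needs the lenient reading.

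**The case for a change.** The best case for a change is that the rule is stated twice, the statements are not logically equivalent, and the unassigned exits are discretionary in an unblinded single-arm trial. Section 13.1 itself mentions a change of diagnosis as a reason for later ineligibility, so this exit is foreseen. One boundary patient could decide the result, and a short clause would close the gap.

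The textual point stands: no section gives an endpoint status for these three exits. The probabilities stand as well, for the assumed numbers of removals. The practical consequence is weaker. Removal may be from only part of the study, and an ineligible patient may be kept on, so many of these patients would still be followed and classified by outcome. Section 9.2.6 expects almost all patients to complete therapy. An analyst facing the 16 + 8 + 1 case would have to claim success with 16 successes against a stated requirement of 17, which the main clause does not allow.

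Replacement of a patient found ineligible after entry is also unwritten. Section 1.0 speaks of 25 eligible patients and Section 14.0 of 25 enrolled, but Section 15.2 requires eligibility to be confirmed at registration, so the two need not conflict. Counting such a patient as a failure gives 0.032 and 0.77; replacing the patient gives 0.054 and 0.85, provided removal is unrelated to outcome. That is a choice between two defensible conventions, not an error in the rule. Requiring failure without replacement would cost power.

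A broader rewrite could also do harm. Counting as a success anyone known to be alive and free of local failure would clash with the existing sentence that makes toxicity removals failures, because a patient removed for toxicity may be failure-free at one year.

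**Conclusion.** The concern does not call for a change. The bracketed failure list is incomplete, but the main clause already gives one answer: a patient removed and no longer followed is not among the 17. The sample size, the cut-off and the printed error rates (0.054 and 0.149 exact) are unaffected. The remaining gap is a classification that an analyst following the rule as written would fill in the conservative direction.

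This rests on reading the bracket as a restatement of the main clause, which its own wording supports, and on there being no replacement other than for reasons unrelated to outcome. If no patient leaves by these routes and goes unfollowed, the two forms coincide exactly. If one or two do, the rule is stricter than printed (size 0.032 or 0.017), with power 0.77 or 0.65. The plan already accepts that kind of loss for toxicity removals and losses to follow-up.
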